## VI. RISKS AND DISCOMFORTS

Participants will be told that they can stop study participation at any time for any reason. Study information and all other personal and identifying information will be kept on a password-protected computer within the secure Partners firewall. All research-related records initiated as a result of a subject's participation in this study that reveal the subject's identity will remain confidential except as may be required by law. Data obtained from this study will not identify the subjects individually. Subjects will be assigned ID numbers, and data obtained may be published, but published data will not identify individual participants.

## **Risks of taking buspirone**

Buspirone can cause one or more of the side effects listed below: Common side effects (experienced by 2 to 12 out of every 100 subjects in previous studies):

- nausea and vomiting
- headache

- dizziness
- drowsiness
- fatigue
- weakness
- numbness
- difficulty sleeping
- depression
- excitement

Less common side effects (experienced by 1 out of 100 subjects):

- Skin rash
- itching
- fast or irregular heartbeat
- blurred vision
- unusual movements of the head or neck muscles

### Pregnancy

The effects of buspirone to an embryo or fetus are unknown and may be harmful. Therefore, individuals who are pregnant cannot take part in the study. The research coordinator will complete the pregnancy screening form with women of childbearing age. During the assessment visit, if the subject is a menstruating female, the pregnancy screening form will be completed by a member of study staff. She will be asked if she is pregnant or if there is any possibility that she may be pregnant, if she is experiencing a late menstrual period, the date of her last menstrual period, and about any contraceptive use. If she confirms that she is not pregnant and there is no possibility that she may be pregnant, a urine pregnancy test will be performed. If the test is negative, we will proceed.

Some subjects may feel uncomfortable when asked to answer detailed questions. Subjects may refuse to answer any of these questions. During the driving simulation, there is a chance that subjects may experience simulator sickness that is similar to motion sickness. Subjects may choose to stop their participation at any time.

The Principal Investigator will be available 24 hours per day via pager to respond to all reports of adverse events, including those that emerge outside of regularly scheduled visits. Adverse events and unanticipated problems will be reported to the PHRC according to current guidelines. We will follow and adhere to all guidelines as defined and outlined on the Partners Human Research Committee website: http://healthcare.partners.org/phsirb/adverse\_events.htm.

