## III. SUBJECT ENROLLMENT

We propose to enroll 24 adult drivers with HF-ASD. Subjects will be males and females, ages 18-45, with a diagnosis of DSM-V Autism Spectrum Disorder. Potential subjects will be recruited from advertising in the local media (newspapers, radio, etc.), MBTA advertisements, flyers posted in the local community and on college campuses, and through the MGH recruitment website, Rally. Potential subjects may also be recruited from local associations that provide programming for individuals with HF-Autism Spectrum Disorder (e.g. AANE, Aspire) or through outpatient clinics at MGH that service individuals with HF-ASD. If a potential subject expresses interest to participate in the study via email, the coordinator will reply and instruct the subject to review the Partner's required language surrounding encrypted and unencrypted emails and will verify their preference prior to proceeding with email communication.

A brief phone screen will be completed with subjects who are interested in participating in the study by a member of study staff. The phone screen asks some questions regarding medical and psychiatric history. If the subject is eligible after the screen, a member of study staff will schedule a time for them to come into the office.

Informed consent will be obtained by a licensed physician investigator prior to the performance of any study procedures. The informed consent will be used to explain, in simple terms, the risks and benefits of study participation to the subject. The subjects may take as much time as they feel necessary to consider their participation in the study, as well as consult with their family members or a physician.

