### IV. STUDY PROCEDURES

Completion of this study will be dependent on the availability of the participant and includes a clinical assessment visit at Massachusetts General Hospital and two driving simulation visits (approximately 1.5 hours each) at Massachusetts Institute of Technology.

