# VIII. MONITORING AND QUALITY ASSURANCE

The principal investigator will be responsible for monitoring and ensuring the integrity of the data and adherence to the IRB-approved protocol. He will review any questions or concerns regarding data collected. Each staff member will undergo focused training on each task for which they are responsible and will perform quality control for others similarly engaged.

The study clinicians, research coordinator, and Principal Investigator will monitor study progress including enrollment, adherence to inclusion/exclusion criteria and study protocol, as well as any adverse events. The Principal Investigator will be responsible for ensuring that adverse events are reported to the Partners Human Research Committee in compliance with requirements. Any changes to the protocol will be made in accordance with local IRB policies.

Any paper material, including the names of subjects or other identifying information (e.g., consent forms and check requests) will be locked up and will be accessible only by study staff. Digital material including the names of subjects or other identifying information (e.g., subject tracking logs) will be kept in password-protected files on protected servers accessible only to departmental staff. All study materials, such as rating scales and neuroimaging data, will be labeled with ID numbers only and will not include identifying information.

Data for all scales collected at the MGH will be entered in RedCap, a platform for electronic data capture that streamlines data collection and management, and ensures data integrity, resulting in improved data quality.

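### The only dated pregnancy check in the supplied text is at the assessment visit; no re-check is scheduled before the first trial-supplied buspirone dose, and the interval between them has no limit

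*Combined protocol and SAP*

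**What the plan says.** Section VI (Pregnancy) gives possible fetal harm as the reason for the exclusion and concludes that "individuals who are pregnant cannot take part in the study". Pregnancy is also listed among the exclusion criteria in Section III.

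The same part of Section VI describes the check. One sentence carries no date: "The research coordinator will complete the pregnancy screening form with women of childbearing age". The next one is dated: "During the assessment visit, if the subject is a menstruating female, the pregnancy screening form will be completed by a member of study staff". The questions cover current or possible pregnancy, contraceptive use, and "if she is experiencing a late menstrual period, the date of her last menstrual period". A woman who says that she is not and could not be pregnant then has a urine test, and "If the test is negative, we will proceed".

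Section IV sets the dosing schedule. Under Driving Simulation Visits, A-B subjects receive the drug when the assessment visit ends but hold it until two days before drive 1. B-A subjects start two days before drive 2. Their drug is handed over after drive 1 or, if no MGH staff member can attend, sent by courier. The drives are booked after the assessment, and Section IV opens by saying "Completion of this study will be dependent on the availability of the participant".

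**The concern.** A negative urine test describes a woman's status on the day of the test. Here the test belongs to the assessment visit, while first exposure comes at a later date that the plan does not bound. A pregnancy that starts in between, or that was too early to detect at the assessment, would be found only if the woman noticed it and reported it.

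The plan itself treats possible fetal harm as a reason to exclude and to test. If that protection is meant to apply at dosing, a result of unlimited age does not reliably provide it. The stake is participant safety only. No estimand, sample size, error rate or model depends on this point.

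**Working it through.** No statistical formula applies and the plan gives no figure to reproduce. The check is a timeline and a search of the supplied text for any later pregnancy step.

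**Inputs**
- Form and urine test: assessment visit, call it day 0 (Section VI, Pregnancy).
- Drives 1 and 2: days T1 and T2, set by participant availability, with no visit windows (Section IV).
- First trial-supplied dose: two days before drive 1 (A-B) or two days before drive 2 (B-A) (Section IV, Driving Simulation Visits).
- Dosing: 5 mg twice daily for two days, then one 5 mg dose an hour before the drive (same place).
- Planned size: "We propose to enroll 24 adult drivers with HF-ASD", half in each sequence (Sections III and IV).

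**Gap from test to first dose**
- A-B: T1 − 2 days.
- B-A: T2 − 2 days.
- Difference at the same T1 and T2: (T2 − 2) − (T1 − 2) = T2 − T1.

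When the drug is handed over after drive 1 and then taken on the two days before drive 2, T2 − T1 is at least about 2 days. No upper limit is stated. T1 and T2 are not given, so neither gap can be put in days. The comparison of sequences holds at equal spacing. Without visit windows, one A-B subject's T1 can fall later than another B-A subject's T2.

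**Exposure**
- Doses: 2 days × 2 + 1 = 5.
- Total: 5 × 5 mg = 25 mg.
- Subjects per sequence: 24 / 2 = 12.

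**Steps between the assessment and the first dose**

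| Step | What Section IV describes | Pregnancy check? |
|---|---|---|
| Reminder by phone or email | Taking the drug, and when | None stated |
| B-A hand-over after drive 1 | Drug plus dosing dates and times | None stated |
| B-A courier shipment | Delivery notice, dosing instructions | None stated |
| Drive visit | Questionnaires, sensors, simulation | None stated |

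A check at the medicated drive would in any case come after dosing had begun. A check at drive 1 in B-A would come before dosing but would leave the interval from drive 1 to drive 2 open.

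The number of women enrolled and the visit intervals are not in the documents, so no probability of an unrecognised exposure is calculated.

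**The case against.** **The existing gate is not trivial.** A woman must say that there is no possibility of pregnancy, answer questions on periods and contraception, and test negative. Exposure is very short, and the documents state no re-test standard that a single screen would breach. This stands as a limit on severity. It does not show that the result is still current at dosing, and the plan asks about contraception without requiring it.

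**The undated coordinator sentence might be a second check.** It differs from the dated one in who completes the form and in how the women are described. Reading both as the same form is natural, but it is an inference. Either way, an undated form does not establish a check before the first dose.

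**A check may exist elsewhere.** The consent pages and the simulation protocol that the MIT IRB reviews are not in the file. A reader might infer that the trial has no later pregnancy check at all. The documents do not support that, and the point is confined to the supplied text.

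**Staff oversee eligibility.** Section VIII has staff monitor "adherence to inclusion/exclusion criteria and study protocol, as well as any adverse events". A reader might infer from the missing re-check that the plan would allow a woman known to be pregnant to be dosed. It would not, because the exclusion still applies. But general oversight cannot reveal a pregnancy that the woman herself has not recognised.

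**B-A is not always the longer wait.** A reader might infer that every B-A woman waits longer than every A-B woman. Counting two open-ended intervals against one does not measure their length, so only the equal-spacing comparison stands. The courier's shipping date is also not stated, so nothing here relies on it.

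**Conclusion.** The point holds in this form: in the supplied text, the only dated pregnancy check can be of any age when the first trial-supplied dose is taken, and no step is scheduled to bring it up to date. This goes beyond missing detail, because staff who follow the plan as written would rely on that one result.

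The magnitude is low (25 mg over 5 doses, no effect on any analysis), and the change is worth making because it is specific and inexpensive. The conclusion rests on two assumptions: that the undated form sentence does not denote a separate pre-dose check, and that no such check is in the documents not supplied. It does not apply in the same way to women already taking prescribed buspirone, for whom the trial does not begin exposure.

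**What to change.** Add one rule to Section VI (Pregnancy), cross-referenced from Driving Simulation Visits in Section IV. It would cover both sequences and apply to women of childbearing age not already taking buspirone:

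1. Re-ask the existing screening-form questions at a reminder contact made before the first dose, which falls at breakfast two days before the medicated drive. Require her reply before she doses, since the reminder may be an email.
2. If pregnancy is possible, or if the last negative test is older than an interval the sponsor sets, she does not take the drug until a urine test is negative. The test can be done in person or with a home strip. The rule applies wherever the drug is, including A-B women who already hold it and B-A women who receive it by courier.

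The reminder may need to go out earlier than now, with a reply obtained and recorded. A few low-cost urine strips are needed, a drive may occasionally be rescheduled, and a short amendment is required. The number of strips depends on the chosen interval and on the answers given, so no upper bound is offered. The rule reduces the gap but cannot close it entirely, because a very early pregnancy can still be missed.

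If the MIT protocol already has a pre-dose check, a cross-reference and the timing rule are enough.

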## VII. POTENTIAL BENEFITS

There may be no direct benefit to subjects participating in this study. Potential benefits to the participants include education about ASD, a trial of medication that could be continued after the study, and the opportunity to contribute to medical science and thus help others with ASD.

# VIII. MONITORING AND QUALITY ASSURANCE

The principal investigator will be responsible for monitoring and ensuring the integrity of the data and adherence to the IRB-approved protocol. He will review any questions or concerns regarding data collected. Each staff member will undergo focused training on each task for which they are responsible and will perform quality control for others similarly engaged.

The study clinicians, research coordinator, and Principal Investigator will monitor study progress including enrollment, adherence to inclusion/exclusion criteria and study protocol, as well as any adverse events. The Principal Investigator will be responsible for ensuring that adverse events are reported to the Partners Human Research Committee in compliance with requirements. Any changes to the protocol will be made in accordance with local IRB policies.

Any paper material, including the names of subjects or other identifying information (e.g., consent forms and check requests) will be locked up and will be accessible only by study staff. Digital material including the names of subjects or other identifying information (e.g., subject tracking logs) will be kept in password-protected files on protected servers accessible only to departmental staff. All study materials, such as rating scales and neuroimaging data, will be labeled with ID numbers only and will not include identifying information.

Data for all scales collected at the MGH will be entered in RedCap, a platform for electronic data capture that streamlines data collection and management, and ensures data integrity, resulting in improved data quality.

